IT Baclofen Drug Distribution Pilot Study: Proposal to Medtronic

Goal:

While ITB therapy is commonly recommended for treatment of severe spasticity due to a variety of diseases, the location of optimal drug (baclofen) delivery has not been defined in a controlled study. Furthermore, the cost of pharmacological management in these patients is significant, and optimal location for drug delivery through an implantable drug pump may have significant impact on the cost burden of maintenance refills. It is the goal of this pilot study to determine whether there is a significant therapeutic advantage to place the ITB catheter within the cervical, thoracic or lumbar region of the spine. It is also a goal of this pilot study to determine whether the origin of spasticity influences the effect of Lioresal Intrathecal (baclofen injection) on ITB catheters located in the cervical, thoracic or lumbar regions of the spine. We propose to study the impact of catheter location on the reduction in spasticity within a group of patients who are scheduled for ITB trial. Furthermore, we intend to enroll patients whose spasticity originates from two different mechanisms (SCI causing spastic paraplegia vs. cerebral palsy causing spastic spasticity of spinal and cerebral origin). In studying the impact of catheter location among patients with spinal versus cerebral origin of spasticity, the disease origin may also have a significant impact on baclofen dosing relative to the placement of the catheter.

In addition, the pharmacokinetic half-life and the variability of intrathecal baclofen is poorly understood as data is limited. In order to provide initial data regarding CSF baclofen washout, samples of spinal fluid obtained just prior to- and following IT baclofen administration will be obtained for delayed analysis. The results of these pharmacological analysis may refine the understanding of how quickly baclofen is distributed from a given catheter location, and whether it is affected by catheter location or disease origin. Since multiple catheter locations will be studied within a given patient, it also affords the opportunity to sample small amounts of CSF at key anatomical sites along the spinal axis as an independent secondary study protocol.

Hypotheses:

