- H₀₁: There is no significant ($p > 0.05$) difference in clinical spasticity (as measured by using the Modified Ashworth Spasm Rating Score) when the same amount of baclofen is delivered (50 μ g) to the cervical, thoracic, or lumbar area on separate days.
- H₀₂: There is no significant ($p > 0.05$) difference in the response to Lioresal Intrathecal (baclofen injection) between patients with spinal versus cerebral origin of spasticity relative to catheter tip placement.

Specific Aims:

1. Measure the degree of spasticity based on the Modified Ashworth Scale for Grading Spasticity in patients undergoing daily, single ITB bolus injections through an intrathecal catheter located in the mid-cervical (C4), mid-thoracic (T3), thoraco-lumbar (T10) and upper lumbar (L2) regions.
2. Measure the Spasm Rating of patients undergoing daily, single ITB bolus injections through an intrathecal catheter located in the mid-cervical (C4), mid-thoracic (T3), thoraco-lumbar (T10) and upper lumbar (L2) regions.

3. Sample CSF at each of the catheter tip locations just prior to ITB injection. Sample CSF at 1, 5, 10, 20, 60 min following ITB administration.
4. Each subject will receive prophylactic antibiotics for the duration of the IT catheter placement.

Methods:

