Subjects who have spasticity and have consented for a trial of ITB therapy as part of a normal therapeutic evaluation, will be asked to enroll in this study. As a pilot study, we are interested in observing significant changes ($p < 0.05$) in either Ashworth Rigidity or Spasm scores related to catheter tip location along the spinal axis. Each subject will serve as their own control and will be assessed by the same rater throughout the study. The subjects will initially undergo temporary implantation of an intrathecal catheter placed under sedation or light anesthesia with fluoroscopic guidance. This will be done by the neurosurgeon with the intent of positioning the catheter initially in the mid-cervical region (C4) of the spine. The following day, after sedation / anesthetic effects are worn off, the subject will undergo a spasticity evaluation in the morning prior to ITB injection (See Tables 2 and 3 regarding Modified Ashworth and Spasm rating scores). Then a 50 microgram (μg) dose of IT baclofen will be injected into the CSF through the catheter. Samples of CSF (3cc) will be withdrawn from the IT catheter just prior to injection and at 10, 30, 60, 120, and 360 min following the ITB injection. The rater (Nurse Practitioner) will perform an Ashworth and Spasm rating exam on the subject at 2, 4, and 6 hours following the ITB injection. Each subject will be allowed to recover and observed overnight in the Clinical Research Center (CRC) at Vanderbilt University.

The following morning, each subject will be brought to the radiology department fluoroscopy room and the IT catheter withdrawn to the next lower level being studied – viz. T3, T10, or L2. Catheter position prior to- and after repositioning will be documented on digital radiograph. The subjects will then be returned to the CRC area and dosed with IT baclofen (50 micrograms IT baclofen). The same protocol for assessing spasticity (Ashworth score) and spasms (Spasm rating) will be performed that day associated with the new catheter position. In other words, a spasticity assessment will be performed just prior to injection, and at 2 hour intervals following injection up to 6 hours after injection. Likewise, a CSF sample will be withdrawn just prior to injection, and at logarithmic intervals up to 6 hours following injection. Each CSF sample will be no more than 3 cc and must represent a clean sample of CSF from the subject.

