At the end of the fifth day of study, the IT catheter will be withdrawn and a stitch placed over the hole in the skin. The subject will be allowed to stay overnight for observation and then released the following morning. Implantation of the ITB pump will be determined as usual by the implanting neurosurgeon and his staff (*note: The decision as to whether the subject or the clinical team decides to implant an ITB pump is outside the scope of this project, and would be considered part of their routine medical care following the trial of ITB*).

Selection of subjects. We will attempt to enroll ten subjects for each disease category by the end of two years. A total of 20 subjects would be enrolled to complete this study. We wish to enroll subjects with similar mechanisms of spasticity for each disease category. Our initial disease categories will involve subjects who have spasticity from very different mechanisms to determine if ITB dosing is significantly different due to origin of spasticity. One group of subjects would have spasticity due to spinal cord injury and are paraplegic, thereby recognizing that their spasticity originates from the lower half of the spinal cord in general. Another group of subjects would have spasticity due to cerebral palsy and are

quadriparetic, thereby recognizing that their spasticity originates from loss of upper motor neurons as a result of cerebral disease (typically associated with a perinatal infarct). Other disease categories, such as cervical spine SCI, stroke, hereditary spastic paraparesis, multiple sclerosis, can be considered in the future if a significant difference ($p < 0.05$ on ANOVA analysis) exists between the two broad categories represented in this pilot study.

There may be reasons why subjects may not be able to complete the study. Some foreseeable reasons include:

- Intradural blockage that prevents advancing the IT catheter to the level of C4, verified by a total MRI of the spine (Cervical, Thoracic, and Lumbar levels), without contrast injection, sagittal views only.
- Significant left over effect of the previous day's administration of IT baclofen thereby prevent a detectable change in spasticity in subsequent injections
- Allergic reaction to IT baclofen
- Withdrawal of the subject from the study
- IT catheter malfunction
- Significant headache from CSF withdrawal
- CSF leak that is intolerable (headache or otherwise) from the IT catheter entry site

Results Anticipated:

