The data will be collected according to the following schedule per patient.

Table 1. Study variables and the timing of data collection. Each table is for a specific catheter location within a given patient. This table, for example, would be filled out 4 times corresponding to the four different catheter locations studied each day.

Time	Catheter Location	Modified Ashworth Score	Spasm Score	CSF Sample
Baseline	C4, T3, T10, L2	0-4	0-4	3cc
Injection (50µg)	-	-	-	-
1 min	-	-	-	3cc
2 min	-	-	-	3cc
10 min	-	-	-	3cc
20 min	-	-	-	3cc
60 min	-	-	-	3cc
2 hours (120min)	-	0-4	0-4	-
4 hours (240 min)	-	0-4	0-4	-
6 hours (360 min)	-	0-4	0-4	-
Total				18 cc / day

Table 2. Modified Ashworth Scale for Grading Spasticity

Grade	Clinical Rating of Tone
0	No increase in tone
1	Slight increase in muscle tone, manifested by a catch and release, or by minimal resistance at the end of the range of motion when the affected

	part(s) is moved in flexion or extension
1+	Slight increase in muscle tone, manifested by a catch, followed by minimal resistance throughout the remainder (less than half) of the ROM
2	More marked increase in muscle tone through most of the ROM, but affected part(s) easily moved
3	Considerable increase in muscle tone, passive movement difficult
4	Affected part(s) rigid in flexion or extension

[figure not shown]
Table 3. Penn Spasm Frequency Scale

Spasm Score	Spasm Frequency
0	No spasms
1	Mild spasms induced by stimulation
2	Infrequent full spasms occurring less than once per hour
3	Spasms occurring more than once per hour
4	Spasms occurring more than 10 times per hour

Spasm Severity	Severity Rating
1	Mild
2	Moderate
3	Severe

For a given subject, the data will be analyzed for the following effects:

1. What was the effect of identical baclofen doses (50µg) administered at different spinal levels within each subject on rigidity? (expect reduction in score over 4-6 hours with possible return towards baseline at 6-10 hours)
2. What was the effect of identical baclofen doses (50µg) administered at different spinal levels within each subject on spasms? (expect reduction in score over 4-6 with possible return towards baseline at 6-10 hours)
3. Is there a significant difference in location of the catheter on the maximum reduction in either spasticity or spasm scores? (expect this to show as the largest “dip” in scores on 3D graph)

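### Catheter level and study day are completely confounded, so the planned location ANOVA tests level and day together, and H01 and its conclusions should say so

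*Combined protocol and SAP*

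**What the plan says.** The Goal section sets out to learn "whether there is a significant therapeutic advantage to place the ITB catheter" in the cervical, thoracic or lumbar spine. H01 compares the same 50 µg dose delivered "to the cervical, thoracic, or lumbar area on separate days". Methods speaks of changes in "scores related to catheter tip location along the spinal axis" and adds: "Each subject will serve as their own control".

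Methods places the catheter first at C4. Each later morning the plan has "the IT catheter withdrawn to the next lower level being studied". The Procedure/Activity table fixes the days: C4 on Day 2, T3 on Day 3, T10 on Day 4, L2 on Day 5. No second sequence, repeated level or control day is described. Inability to reach C4 is listed as a reason for not completing, so the slightly loose wording of the table rows does not create another order.

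Under Results Anticipated, each disease group gets an ANOVA of greatest change against location, for Ashworth and spasm scores. Question 4 there asks about day-to-day washout, looking for baselines that fall each day, and the results table has a between-day Ashworth row. The one consequence stated for a positive finding concerns the size of the daily dose; nothing links it to how the location result is read.

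**The concern.** Where every subject follows one sequence, a difference between levels is also a difference between days. Anything that changes the response over Days 2 to 5 enters the location comparison in full: residual drug, tolerance, cumulative CSF loss, or a shift in rating or setting. Having subjects act as their own controls removes differences between people, not between days.

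The plan itself foresees one such effect. Among the reasons for non-completion it lists left-over drug from the day before, which would "thereby prevent a detectable change in spasticity in subsequent injections". That is a day effect on the change score, the quantity the ANOVA analyses.

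At stake is the pilot's first goal. As written, a significant result would be reported as an advantage of a level, and a null result as no difference between levels, when either could come from day.

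**Working it through.** The plan states no power, SD or effect size, so there is no figure of its own to reproduce.

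**1. What moves with level** (Methods, Table 1, Procedure/Activity table). Each dosing day has six CSF samples of 3 cc: 6 × 3 = 18 cc, as Table 1 totals. The timing lists in Methods and Table 1 differ, but both give six samples.

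| Level | Day | Earlier doses | CSF already removed (at most) |
|---|---|---|---|
| C4 | 2 | 0 | 0 cc |
| T3 | 3 | 1 | 18 cc |
| T10 | 4 | 2 | 36 cc |
| L2 | 5 | 3 | 3 × 18 = 54 cc |

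**2. Can level and day be separated?** This needs no assumed variance.

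- Subject + location, 20 subjects: 20 + 3 = 23 columns, rank 23.
- Adding day: 23 + 3 = 26 columns, rank still 23.
- One group of ten: 10 + 3 + 3 = 16 columns, rank 13.
- Adding group-by-location to the 20-subject model: rank 26. Adding day and group-by-day then gives 32 columns, rank still 26.

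The three location degrees of freedom are the three day degrees of freedom. Nothing is left to estimate one after the other.

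**3. Does the same-day baseline cure it?** Let the pre-injection score on day d be B − a(d) and the lowest post-injection score be B − a(d) − R(d). The change is R(d). A purely additive shift a(d) cancels; a day effect on the response R(d) does not. A response proportional to the baseline turns even a baseline shift into a change in R(d).

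**4. How large could it be?** Illustration only. From the documents: n = 10 per group, 0-4 scores, p < 0.05. Assumed: the repeated-measures form of the ANOVA, F(3, 27) (the plan says only ANOVA); baseline mean 3, SD 0.5; rating SD 0.4 or 0.8; whole-number scores; change = pre-injection minus lowest of three post-injection scores; response either half the baseline or a fixed 1.5 points; washout check = the same ANOVA on the daily baselines. Attrition for left-over effect is not modelled. 8,000 simulated trials per cell, no location effect, stable baseline:

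| Day effect on response | Significant location result, SD 0.4 | SD 0.8 | Washout check positive |
|---|---|---|---|
| +0.2 points per day (L2 looks better) | 34-35% | 12-13% | about 5% |
| −0.2 points per day (L2 looks worse) | 38-43% | 15-16% | about 5% |

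A closed-form check without rating-scale assumptions: for a linear day trend of d within-subject SDs per day, the noncentrality is λ = n × 5 × d², where 5 = 1.5² + 0.5² + 0.5² + 1.5². With n = 10 and critical F(3, 27) = 2.96:

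- d = 0.1: λ = 0.5, rejection 8%.
- d = 0.25: λ = 3.125, rejection 25%.
- d = 0.5: λ = 12.5, rejection 80%.

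**5. What does a positive washout check mean?** With a fixed response, SD 0.4 and a baseline falling 0.3 points per day, the check is positive in about 90% of trials, while the location test rejects in about 6%, close to nominal. A positive check is therefore compatible with a sound location comparison. A negative one, by the table in step 4, is compatible with an unsound one.

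**The case against.** The sequence follows from placing one catheter at C4 and withdrawing it stepwise, and this is a 20-subject pilot. The plan is not silent on carry-over: it has a fresh baseline each morning, one rater, overnight recovery, an explicit washout question, and pre-dose CSF ("Sample CSF at each of the catheter tip locations just prior to ITB injection"). It expects a "possible return towards baseline at 6-10 hours", so little drug effect may remain the next morning. Subjects with marked left-over effect may not complete at all, which the simulation omits. With ten per group, many null results would arise from low power whatever the day effect.

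Much of this stands. Carry-over may be small, and the washout check is useful against residual drug that lowers the baseline. None of it makes level estimable apart from day, and the check cannot see a day effect on response that leaves the baseline unchanged.

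A reader might go further and infer that a significant washout check rules out a pure location reading. It does not. An additive shift cancels in the change score (steps 3 and 5 of the working), and each day's baseline follows the dose at the level above, so the check is itself aliased with the previous level.

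**Conclusion.** The point holds. The aliasing is exact and rests only on the documented sequence. The ANOVA tests level and day combined, and supports a location conclusion for H01 only on the assumption of no day, order or carry-over effect on the change score, which the plan neither states nor can test.

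The size of any bias is unknown. The 34-43% and 12-16% rates show what an assumed 0.2-point daily effect would do; they do not estimate this trial's error rate.

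Two stronger readings are tempting. One is that a location finding here would probably be false; the documents give no day-effect size, so they do not support that. The other is that H02 fails in the same way; it does not, because a day effect equal in SCI and CP cancels in the group-by-location comparison. Only an unequal one would bias it.

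**What to change.** 1. In H01 and the analysis section, state that the comparison is of level and day combined (C4/Day 2 to L2/Day 5). State also that no advantage of a level, or absence of one, will be claimed without the explicit assumption of no day or carry-over effect on the change score.
2. State that the group-by-location comparison (H02) is free of day effects only if these are equal in SCI and CP.
3. Beside the location result, report by day: number of subjects rated; pre-injection, lowest post-injection and change scores; and pre-dose CSF baclofen. Label the last as descriptive, since it is drawn at that day's tip. State that a significant washout check makes a pure location reading unsafe without further assumptions but does not by itself disprove it, and that a non-significant check does not establish one.

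No change to order, dose or procedures is proposed. The cost is wording plus tables from data already collected. The downside is a weaker H01 claim, and an equal-day-effect assumption for H02 that the study cannot verify.

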4. Is there a “washout” effect from day to day? (if so, expect the baseline scores to be lower each day) If present, this would suggest that the daily dosing is too high.

[figure not shown]

For each group (SCI vs CP), the data will be analyzed as follows:

1. What catheter location caused the greatest change in spasticity scores? (the location of the catheter – C4, T3, T10 or L2 – would be noted and averaged among the ten subjects). Expect that

SCI group would favor greater change when catheter is located at T10 or L2. Expect that CP group might not show a significant difference in catheter location.

2. What catheter location caused the greatest change in spasm scores? (the location of the catheter – C4, T3, T10 or L2 – would be noted and averaged among the ten subjects) Expect that SCI group would favor greater change when the catheter is located at T10 or L2. Expect that the CP group would not have much spasm change based on catheter location.

Parameter	SCI Paraplegic (n=10)	CP Quadriparetic (n=10)
Greatest change in Ashworth Score vs Location	? ANOVA	? ANOVA
Greatest change in Spasm Rating vs Location	? ANOVA	? ANOVA
Difference in Ashworth Score between days (assess washout effect)		

Subject Recruitment and Length of Study:

We expected to be able to recruit 20 patients for this study within two years. The subjects would be solely recruited and managed through the Adult Neurosurgery practice at Vanderbilt. Patients would be approached for enrollment after first choosing to undergo an ITB trial for the treatment of their spasticity.

Procedure/Activity	Frequency
Patient consent	Clinic visit 1 1
MRI Total Spine without contrast	Outpatient Radiology 1
Implantation of intrathecal catheter under light sedation and fluoroscopy guidance to C4	Inpatient MCE Day 1 1 Transfer to CRC after wake-up from MCE procedure (CRC Day 1)
Baclofen Injection (50µg)	Inpatient CRC Day 2
Modified Ashworth Rigidity testing and Spasm rating	Inpatient CRC Day 2 at 2, 4, and 6 hours following injection
CSF Specimen 3cc	Inpatient CRC Day 2 10 min, 30 min, 60 min, 120 min, 360 min
Repositioning of intrathecal catheter to next lower level or T3 under fluoroscopy	Inpatient Radiology Day 3 1 (for this day)
Baclofen Injection (50µg)	Inpatient, CRC, Day 3
Modified Ashworth Rigidity testing and Spasm rating	Inpatient, CRC Day 3 at 2, 4, and 6 hours following injection
CSF Specimen 3cc	Inpatient CRC Day 3 10 min, 30 min, 60 min, 120 min, 360 min

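### Does the by-group washout row need a rule for subjects who stop because of left-over baclofen effect?

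*Combined protocol and SAP*

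**What the plan says.** In the Selection of subjects part of Methods, the plan sets ten subjects per disease category ("A total of 20 subjects would be enrolled to complete this study") and warns that "There may be reasons why subjects may not be able to complete the study". One listed reason is residual effect of the previous dose: "administration of IT baclofen thereby prevent a detectable change in spasticity in subsequent injections". No exit rate, replacement rule or missing-data rule is given.

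Methods asks on each dosing day that "a spasticity assessment will be performed just prior to injection". Table 1 puts a baseline row before the injection row, and its caption says the form "would be filled out 4 times corresponding to the four different catheter locations studied each day". Four pre-dose scores per subject are therefore planned: C4 on Day 2, T3 on Day 3, T10 on Day 4 and L2 on Day 5.

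Under Results Anticipated, carry-over (which the plan calls washout) appears twice:

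- Question 4 of the list for a given subject looks for lower baselines from day to day and adds: "If present, this would suggest that the daily dosing is too high".
- The group results table, under columns headed n=10, has a row labelled "Difference in Ashworth Score between days (assess washout effect"), with blank cells. The list that begins "For each group (SCI vs CP), the data will be analyzed as follows" has two numbered questions, both about catheter location and neither about washout.

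**The concern.** Carry-over shows as a falling pre-dose score. If a subject leaves because carry-over is large, that subject's later pre-dose scores do not exist, and the by-group row rests on those who had less of it. A row built from completers would then lean towards finding no washout. With ten subjects per group, losing two or three in this way could decide whether a fall is seen at all. The plan foresees this kind of exit and has a row for the quantity concerned, but does not say how the two meet. Because the rating is tied to the injection, one could also ask whether the score is kept on a day when a subject stops before being dosed.

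**Working it through.** **Plan figures.** 2 × 10 = 20 agrees with the stated total. The documents give no SD, exit rate, carry-over size or power, so there is no washout figure to reproduce. Every effect size below is an assumption.

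**Direction, by algebra.** Let *k* of *n* subjects stop after a fall d_stop, and let the rest complete with a fall d_stay. Let *gap* be how much higher the stoppers started than the completers. For stops at the Day 3 or Day 4 baseline:

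- every subject's last recorded score: d_stay + (k/n)(d_stop − d_stay)
- completers, and subjects with four baselines: d_stay
- raw Day 2 mean minus raw Day 5 mean: d_stay + (k/n) × gap

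Take n = 10, k = 3, d_stop = 2.0 and d_stay = 0.25. The last-score fall is 0.25 + 0.3 × 1.75 = 0.775. Completers give 0.25. Raw means give:

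- 0.25 with equal starting scores
- 0.25 − 0.15 = 0.10 if stoppers started 0.5 lower
- 0.25 + 0.15 = 0.40 if they started 0.5 higher
- 0.25 + 0.60 = 0.85, an overstatement, if they started 2 higher

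The raw mean overstates once the gap exceeds d_stop − d_stay = 1.75. If the stops come at the Day 5 baseline, those subjects have all four scores, and both the four-baseline and raw summaries return 0.775. So the direction is certain for completers, conditional for the four-baseline set, and likely but not certain for raw means.

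**Size, by simulation.** Assumed: Day 2 mean 3, SD 0.6; fall per day 0.2, SD 0.15, so the true Day 2 to Day 5 fall is 3 × 0.2 = 0.60. Exit occurs when the recorded fall passes a threshold, and the last pre-dose score is kept. Estimated fall at 10 / 20 / 30% exit:

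| Summary | Rating error SD 0.2 | Rating error SD 0.4 |
|---|---|---|
| Four baselines | 0.584 / 0.550 / 0.507 | 0.562 / 0.515 / 0.462 |
| Raw day means | 0.587 / 0.562 / 0.529 | 0.584 / 0.564 / 0.542 |
| Completers | 0.497 / 0.416 / 0.340 | 0.467 / 0.365 / 0.270 |
| Likelihood model | 0.60 | 0.60 |

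The raw-mean error runs from 0.60 − 0.587 = 0.013 to 0.60 − 0.529 = 0.071. The completer row is far lower partly because it also discards Day 5 scores already recorded from subjects who then stop.

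**Detection in a group of ten** (p < 0.05). Full data give 89% (rating error 0.2) or 65% (0.4).

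| Exit | Four baselines | Mixed model | Difference in points |
|---|---|---|---|
| 10% (1 of 10) | 87.5% or 60.0% | 88.6% or 60.4% | 1.1 or 0.4 |
| 30% (3 of 10) | 76.8% or 42.8% | 86.7% or 57.6% | 9.9 or 14.8 |

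The mixed-model figures rest on 700 simulated groups. The Monte Carlo standard error at 60% is √(0.6 × 0.4 / 700) = 1.9 points, and at 88% it is √(0.88 × 0.12 / 700) = 1.2 points. The differences at 10% exit are within that noise.

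**What the inference rests on.** The remark on daily dosing is attached to question 4 for a given subject. Someone who stops with a low pre-dose score shows carry-over there directly. The group row carries no test, threshold or decision.

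**The case for a change.** The strongest reply is that the plan itself expects to lose subjects on the quantity the row estimates, that the likely error runs towards no washout, and that the remedy is cheap. The omission stands, and so does the direction for a completers-only row. At 30% exit the four-baseline set does lose about 10 to 15 points of detection against a mixed model. If the last pre-dose score were thrown away, even the model would be 8–42% short.

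The rest is weaker. The losses arise under choices the plan does not make: it does not restrict the row to completers or discard a recorded baseline. Methods and Table 1 both place the pre-dose score before the injection, so it would normally exist when a decision to stop is taken. The Procedure/Activity schedule lists only the 2, 4 and 6 hour ratings, but that is a separate mismatch. The 30% scenario means three of ten subjects per group leaving for this one reason, and nothing in the documents supports that rate. The model is not free of error either: if exit follows the underlying effect and not the recorded score, it stays 0.3–6% short. The simulations also treat the score as continuous, whereas Table 2 gives ordinal grades (0, 1, 1+, 2, 3, 4), so a fall of 0.2 per day might not be visible on the scale.

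**Conclusion.** No change to the plan is called for. This is missing detail in a descriptive row of a 20-subject pilot, and an analyst would fill it sensibly: take each subject's change from the Day 2 pre-dose score, use every score recorded, and state how many stopped for residual effect and when. Nothing in the plan prevents that or points the other way.

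Under the assumed values, raw day means are 0.01–0.07 points short, well inside the mixed model's SD of 0.17–0.25 in a group of ten, and at 10% exit the model gains essentially nothing in detection. The gain becomes clear only at 30% exit. If exit is unrelated to carry-over, there is no bias. These sizes depend on invented exit rates, falls and rating errors, and would change with them. The conclusion rests more on the text: no rule drops these subjects, the row supports no stated decision, and the dosing inference is drawn subject by subject. The location comparison is not touched by this point.

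### The plan describes no masking of the rater to catheter level or earlier scores, so expectation could contribute to a location effect in SCI and a false difference between origins

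*Combined protocol and SAP*

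**What the plan says.** - **Rater.** Methods: "Each subject will serve as their own control and will be assessed by the same rater throughout the study". The role is given in the singular: "The rater (Nurse Practitioner) will perform an Ashworth and Spasm rating exam on the subject", at 2, 4 and 6 hours after injection. There is also a rating before each day's injection.
- **Recording.** Results Anticipated, Table 1: "Each table is for a specific catheter location within a given patient". Its columns include catheter location, Ashworth score and spasm score, with baseline and the three post-dose ratings in the same table. "This table, for example, would be filled out 4 times corresponding to the four different catheter locations".
- **Scale.** Table 2 separates Ashworth grades by the examiner's impression of resistance, for example "Slight increase in muscle tone, manifested by a catch and release".
- **Expected results.** In the group analysis (SCI vs CP), for spasticity scores: "SCI group would favor greater change when catheter is located at T10 or L2". For the other group: "Expect that CP group might not show a significant difference in catheter location". The same pattern is stated for spasm scores.
- **Order.** Methods: "the IT catheter withdrawn to the next lower level being studied". The procedure table gives C4 on day 2, T3 on day 3, T10 on day 4 and L2 on day 5 for every subject.

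No section mentions a masked rater, a coded form or an independent assessor.

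**The concern.** Keeping one rater per subject removes differences between raters. It does not remove a lean that varies with level or diagnosis, because such a lean falls within the subject, where the location comparison is made. The pattern the plan expects (a location effect in SCI, little or none in CP) is also the pattern that would reject both null hypotheses. A rater who knew the level and shared the expectation could push the data towards rejecting H01 in SCI and towards rejecting H02.

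The plan tests at p<0.05 and makes extension to other disease categories depend on a significant difference between the two groups. A false difference would therefore steer later work.

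**Working it through.** The plan has no figure to reproduce: the total is simply 10 + 10 = 20, with no effect size, SD or power. The calculation below only illustrates how sensitive the tests are to a lean.

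**Inputs from the documents.** 10 SCI and 10 CP subjects; four levels, each tested once per subject; ANOVA; significance at 0.05; expected levels T10 and L2 in SCI.

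**Assumptions (not in the documents).** No true location effect. One change score per subject and level. The lean adds b grades of improvement at T10 and L2, in SCI only and in post-dose scores only. Within-subject SD of 0.5, 0.7 or 1.0 grade. Repeated-measures ANOVA with independent, equal-variance errors.

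**SCI location test, F(3, 27).** Two of four levels are shifted by b, so each level mean lies b/2 from the SCI average. The noncentrality is λ = 10 × 4 × (b/2)² / SD² = 10b²/SD².

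**Location-by-origin test, F(3, 54).** With the shift in SCI only, each of the 8 group-by-level cells has an interaction effect of size b/4. Then λ = 10 × 8 × (b/4)² / SD² = 5b²/SD².

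**Half-grade lean, b = 0.5.** The numerators are 10 × 0.25 = 2.5 and 5 × 0.25 = 1.25.

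| SD | λ, SCI location | Chance of p<0.05 | λ, location by origin | Chance of p<0.05 |
|---|---|---|---|---|
| 0.5 | 2.5/0.25 = 10.0 | 69% | 1.25/0.25 = 5.0 | 41% |
| 0.7 | 2.5/0.49 = 5.10 | 39% | 1.25/0.49 = 2.55 | 22% |
| 1.0 | 2.5/1.00 = 2.5 | 21% | 1.25/1.00 = 1.25 | 13% |

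**Quarter-grade lean, b = 0.25.** The SCI location test gives 21%, 12% and 8% at the same three SDs; the location-by-origin test gives 13%, 9% and 7%.

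With b = 0 both tests return the nominal 5%. A simulation of the SCI location test (20,000 runs per setting, SD 0.5 and 0.75) agreed with the noncentral F results to within about 0.3 percentage points.

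A location test pooled over all 20 subjects, which is closer to the wording of H01, has the shift diluted to b/2. Its λ is 20 × 4 × (b/4)² / SD² = 5b²/SD², again on 3 and 54 df, so the figures match the interaction column. The 69%, 39% and 21% apply only to the SCI-only ANOVA in the plan's group table.

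**The case against.** **The documents do not show that bias will occur.** A reader might infer from Table 1 that the rater fills it in, sees the level and the day's earlier scores on it, and has been told which levels should win. No section says so. Table 1 is presented as a data-collection schedule and also holds injection and CSF rows. Nor does the plan say outright that one person rates all 20 subjects; it says each subject keeps the same rater. This stands. The gap is a missing safeguard, not a demonstrated bias.

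**The scales are not equally exposed.** Spasm frequency grades 2 to 4 in Table 3 are anchored to hourly counts. This stands: the argument about judgement applies mainly to the Ashworth grades and to the mild, moderate and severe spasm ratings.

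**Change scores offer some protection.** The plan analyses change, and the subject is rated before each day's injection with the catheter already at that day's level. A lean present equally before and after the dose cancels. This stands, and it is why the illustration confines the lean to post-dose scores. Lower baselines on later days, which the plan itself raises as a possibility, would also leave less room for a drop at T10 and L2; the illustration ignores this.

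**A new form cannot mask a fixed order.** Level follows from study day, so a rater who learns the sequence can count days. Even perfect masking would not separate level from day or carry-over. A reader might infer that masking would make a positive location result interpretable; it would not. This stands and limits what the fix can claim. It does not justify leaving level and earlier scores open to the rater, since concealing them costs little and still reduces anchoring on previous grades.

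**This is a small pilot, and pump decisions lie outside it.** That is true and limits the severity. The plan still uses a significance test to decide on further study.

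**Conclusion.** The concern holds as an absence of described masking. The route to bias is specific: a lean confined to post-dose scores, in SCI, at the levels the plan expects to do best. If that lean averaged half a grade with no true effect, the false-positive rate would be 21% to 69% for the SCI location ANOVA and 13% to 41% for the location-by-origin test, against a nominal 5%. At a quarter grade the ranges are 8% to 21% and 7% to 13%. The size of the lean and the SD are assumptions, so these are conditional rates, not estimates of what will happen.

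The change is worth making because it is cheap and touches both hypotheses. It is not the only limit on the location comparison, nor the deepest: level is confounded with day and carry-over whatever the rater knows.

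**What to change.** 1. Record each rating on its own sheet, with subject code, time and score only, and collect it straight after the rating so that earlier scores are not in view.
2. Keep level, radiograph and CSF records on a separate sheet held by the dosing staff.
3. Do not brief the rater on the level sequence or the expected results.
4. After each day's 6-hour rating, record the rater's guess of the level, and report the guesses with the results.
5. State in the plan and the report that, because level is tied to study day, these steps reduce but do not remove the rater's knowledge of level, and that a location effect stays confounded with day and carry-over. Report location results as exploratory on both grounds.

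The cost is a revised form, a briefing rule and one extra item per dosing day. No extra subjects or staff are needed, and no dose or clinical procedure changes. The drawback is incomplete masking, which the recorded guesses would help to show.
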